9.12.1 Adverse Events

9.12.1.1 General Principles

All AEs will be coded by primary SOC and PT according to the latest version of MedDRA.

The analysis of AEs will focus on TEAEs. TEAE summary tables will provide summaries of the number and percentage of subjects reporting an AE by SOC and PT. When multiple AEs are reported within an SOC/PT category by a subject, the AE will be included only once per subject per SOC/PT category (subject incidence). For severity, if a subject reports multiple events per SOC/PT over more than one severity category, the event with the highest severity will be reported. Similarly, for study drug relationship, if multiple events are recorded per category, the event with the highest attribution to study drug recorded per subject /category will be reported in the summary tables.

If the severity of AE is not reported, the event will be classified as a Grade 3 (severe) event and clearly footnoted. Imputed severities will also be noted in line listings with the observed and imputed values.

If the relationship to the study drug is not reported for an AE, the event will be assigned a relationship of 'definite' in tables of study-drug related AEs and clearly footnoted. Tables presenting related AEs will include all AEs with relationships of 'possible', 'probable', or 'definite' as assessed by the Investigator, or defined as 'definite' when no investigator assessment is made. Imputed relationships to study drug will also be noted in line listings with the observed and imputed values.

9.12.1.2 Missing or Partial Adverse Event Dates

Refer to Section [9.4.2](#).

9.12.1.3 All TEAEs

An overall summary table of TEAEs will be calculated including the number of TEAEs and subject incidence in each of the following categories:

- Any TEAE.
- Any SAE.

- Any TEAEs leading to death.
- Any TEAE leading to withdrawal from the study.
- TEAEs by severity grade (Grade 1 to Grade 4)
- TEAEs by relationship to study drug (unrelated, unlikely, possible, probable, definite) and pooled study drug related category (related [possible, probably and definite] or unrelated [unrelated, unlikely])
- The number and percent of participants with 0, 1, 2, 3, 4, 5, and > 5 TEAEs, and the mean, median, interquartile range, min and max number of TEAEs per participant.

By severity grade and relationship, if a subject reports more than one TEAE, then that subject will be counted once at the highest severity and/or relationship category.

At the Day 42 output, the summary table will only be issued for data collected up to Day 42 (start dates prior to the Day 42 visit), including TEAEs ongoing at the Day 42 visit. At the Week 16 output, the summary table will be issued for each of these three intervals:

- Day 0 to Day 42,
 - TEAEs with start dates on or after Day 0 but prior to the Day 42 visit, or
 - TEAEs with start dates before Day 0 that were on-going at Day 0, and worsened in severity on or after Day 0 but prior to the Day 42 visit.
- > Day 42 to Week 16,
 - TEAEs with start dates after the Day 42 visit, or
 - TEAEs with start dates prior to the Day 42 visit, were ongoing at the Day 42 visit, and worsened in severity on or after the Day 42 visit.
- Day 0 to Week 16.
 - All TEAEs starting prior to the Week 16 visit, or
 - All TEAEs with start dates before Day 0 that were on-going at Day 0, worsened in severity on or after Day 0 but prior to the Week 16 visit.

The following tables will also be presented for the SfAS:

- TEAEs by SOC and PT
- TEAEs by SOC and PT by severity
- TEAEs by SOC and PT by relationship to study drug
- SAEs by SOC and PT

At the Day 42 output, these tables will be issued for data collected up to Day 42 and for the Week 16 output, for all data collected up to Week 16.

AE data will be listed in full.

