11.2.3 Prohibited Medications

The Investigator will inform subjects of the following prohibited medications which may interfere with efficacy evaluations by masking the effect of treatment:

- subjects must not receive treatment with any scabicide, including permethrin, ivermectin, benzyl benzoate, sulfur, lindane, crotamiton, malathion, tea tree oil, or spinosad, between Screening and Day 28. Note that this includes the use of ivermectin for any approved or unapproved indication.
- subjects must not use topical over the counter or prescription medications used to manage itching (i.e., containing corticosteroids, ferric oxide, crotamiton, calamine etc.) between Day 0 and Day 28.
- subjects must also be advised to avoid contact with any treatments taken by their close personal contacts.

Pruritus management outlined in Section 11.2.2 should be actively followed. However, although scabicides are prohibited medications prior to the Day 28 visit, subject wellbeing is the priority. As this is a single dose treatment study, withdrawing from treatment is not applicable. If scabicides are required for the subject's wellbeing, the subject does not need to withdraw from the study for the Investigator to provide scabicides and subjects should continue on-study if they receive scabicides prior to Day 28 (Section 14). An excessive rate of scabicide administration prior to Day 28 can render the study difficult to interpret. The exposure to scabicides prior to Day 28 will be considered a major protocol deviation and subjects will be considered non-responders for the primary analysis (Section 15.6.8).

11.3 After Day 28

If subjects are positive for scabies mites by microscopy or dermoscopy at Day 28, or their clinical presentation has significantly worsened from Day 0, the subject will be given treatment with a scabicide. In the United States, permethrin 5% cream or spinosad 0.9% lotion should be used according to labelled instructions. In other regions such as Latin America, approved standard of care therapy per local guidelines may be used.

In addition to emollients and over-the-counter antihistamines, subjects may use topical over the counter or prescription medications used to manage itching (i.e., containing corticosteroids, ferric oxide, crotamiton, calamine etc.) after Day 28.

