3 STUDY OBJECTIVES

3.1 Primary Objectives

The primary objectives of the study are:

- To compare the efficacy of a single oral administration of moxidectin for each of the three moxidectin doses to matching placebo with respect to the Day 28 Complete Cure rate.
- To compare the safety of a single oral administration of moxidectin for each of the three moxidectin doses with placebo.

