4 SAMPLE SIZE DETERMINATION

Approximately 200 index subjects will be randomized into one of four cohorts using an equal allocation ratio. Only one subject will be enrolled per household; where more than one household member is screened for the study, the index subject is the youngest eligible member of the household.

The target sample sizes per randomized treatment group are shown in [Table 2](#). The sample size was selected to address the study's primary efficacy objective.

Table 2: Sample Size by Randomized Treatment Group

Randomized Treatment Group	Target Sample Size
Placebo	N = 50
Moxidectin 8 mg, single dose	N = 50
Moxidectin 16 mg, single dose	N = 50
Moxidectin 32 mg, single dose	N = 50

A sample size of 50 subjects per randomized treatment group will yield an approximate power of 75% for the pairwise comparisons of each moxidectin dose group to placebo assuming a placebo Day 28 Complete Cure rate of 40% or less and a moxidectin Day 28 Complete Cure rate of 70% or more. Power calculations for each pairwise comparison were conducted via a Z test for two independent proportions with pooled variance at a two-tailed adjusted alpha of 0.019. The pairwise adjusted alpha of 0.019 is used to control the familywise error rate (FWER) at an overall two-tailed alpha of 0.05 using a large sample approximation to Dunnett's critical value for the 3 pairwise comparisons of each moxidectin dose group to placebo.

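### No adverse event table is cut at the Day 28 visit, when subjects in any arm may receive a scabicide, so later comparisons with placebo mix in other products, unequally by arm if moxidectin works

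*SAP*

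**What the plan says.** One of the two primary objectives in SAP 3.1 is "To compare the safety of a single oral administration of moxidectin for each of the three moxidectin doses with placebo".

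Protocol 11.3 sets what happens at Day 28. If mites are found, or the clinical picture is significantly worse than at Day 0, "the subject will be given treatment with a scabicide". US sites use permethrin or spinosad. "In other regions such as Latin America, approved standard of care therapy per local guidelines may be used"; Protocol 5.2 counts oral ivermectin as standard of care in some places. Topical anti-itch products, including corticosteroids, also become permitted. The rule is the same in every arm. Protocol 11.2.3 allows a scabicide before Day 28 if the subject's wellbeing requires it, and the subject stays on study.

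SAP 8.3 keeps subjects in the group of the study drug they received. SAP 9.12.1.3 then defines the TEAE tables:

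- Overall summary, Day 42 output: one block to Day 42.
- Overall summary, Week 16 output: Day 0 to Day 42, after Day 42 to Week 16, and Day 0 to Week 16.
- SOC/PT, severity, relationship and SAE tables: "these tables will be issued for data collected up to Day 42 and for the Week 16 output", where they cover everything to Week 16.

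The scabicide definition in SAP 7 covers use up to Day 28 only. The safety subgroups in SAP 9.12.8 do not include scabicide use.

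**The concern.** The plan treats scabicide use as the intercurrent event for efficacy (SAP 3.4), but SAP 9.12 has no counterpart for safety. Day 28 is when a second active product can enter any arm. If moxidectin works, it enters the placebo arm more often. From then on the placebo column is partly placebo followed by permethrin, spinosad or a local alternative, and each moxidectin column is partly moxidectin followed by the same products. Even the Day 0 to Day 42 block contains this period. No prespecified TEAE table shows moxidectin against placebo before it begins.

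What is at stake is how a primary objective is read. A difference, or the lack of one, in the Day 42 and Week 16 tables could not be assigned to moxidectin alone. A Day 28 table built later would carry the label that SAP 1.1 gives to any analysis not defined in advance: post hoc and exploratory.

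**Working it through.** **1. Planning figures (SAP 4).** Inputs: "A sample size of 50 subjects per randomized treatment group", "with pooled variance at a two-tailed adjusted alpha of 0.019", "approximate power of 75% for the pairwise comparisons", and a "placebo Day 28 Complete Cure rate of 40% or less and a moxidectin Day 28 Complete Cure rate of 70% or more". The documents state no safety figure, so this step only confirms the rates used below.

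Power = Φ{[0.30 − z·√(2·0.55·0.45/50)] / √[(0.40·0.60 + 0.70·0.30)/50]}, with z = 2.3455 for two-tailed 0.019. This is Φ[(0.30 − 2.3455·0.0995)/0.0949] = Φ(0.702) = 75.9%. The stated 75% is reproduced.

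**2. Nominal time after Day 28.** It makes up 14/42 = 33% of the Day 42 tables and 84/112 = 75% of Day 0 to Week 16. These are shares of calendar time, not of time exposed to a scabicide.

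**3. Who might be treated.** Non-cure at the planning rates is 1 − 0.40 = 60% on placebo and 1 − 0.70 = 30% on moxidectin. Not every non-cured subject meets the Day 28 trigger. Let q be the share who are treated. The documents give no value for q; I assume it is equal across arms. Treated per arm = 50 × non-cure × q.

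| q (assumed) | Placebo, of 50 | Each moxidectin arm, of 50 | Gap (percentage points) |
|---|---|---|---|
| 25% | 7.5 | 3.75 | 7.5 |
| 50% | 15 | 7.5 | 15 |
| 100% | 30 | 15 | 30 |

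With placebo cure at 20% and q = 50%, the counts are 20 and 7.5. If the arms cure equally, the gap is zero.

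**4. Possible shift in TEAE incidence, illustration only.** Let b be the background TEAE risk, equal in all arms, and r the risk that a scabicide produces a TEAE in a subject who would otherwise have none. A subject counts once, so the shift in moxidectin minus placebo is −(1 − b) × r × 0.30 × q. All values of b, r and q are assumptions.

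- b = 40%, r = 5%, q = 50%: −0.60 × 0.05 × 0.30 × 0.50 = −0.45 percentage points.
- b = 20%, r = 20%, q = 100%: −0.80 × 0.20 × 0.30 × 1 = −4.8 percentage points.
- b = 100%, as in study MDGH-MOX-2001, where all 22 subjects had a TEAE: zero for the any-TEAE line.

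The negative sign follows from assuming that a scabicide only adds events. If treating persistent scabies prevents skin events, the sign can reverse.

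**5. Which safety data are exposed.** Routine blood samples end at Day 28 (Protocol 9.4.6), with Week 16 samples only for unresolved abnormalities. Vital signs are summarized by time point (SAP 9.12.2), so Day 14 and Day 28 stand apart from Day 42 and Week 16. The Week 16 ECG comes after Day 28. The exposed data are therefore mainly the TEAEs, plus the Day 42 and Week 16 vital signs and the Week 16 ECG.

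**The case against.** Much can be said for the plan, and most of it limits the point.

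- A reader might infer that all safety output runs undivided. It does not: the overall TEAE summary is split at Day 42 in the Week 16 output, routine laboratory data end at Day 28, and vital signs are shown by visit.
- A reader might infer that scabicide use will be invisible. SAP 9.10 tabulates concomitant medications as n (%) by group, ATC class and preferred term. What is missing is a combined scabicide count placed in time against Day 28.
- A reader might take 60% of placebo and 30% of moxidectin subjects as the numbers treated. That equates failing Complete Cure with needing a scabicide. Complete Cure fails on itch or a single lesion, itch is expected for four to six weeks (Protocol 11.2.2), and the Investigator assessment has a category for residual signs needing no treatment (Protocol 9.4.9). The figures are an upper limit under the planning rates.
- Investigators stay blinded to Week 16, and Protocol Table 10 lets them class a known effect of another drug as unrelated. This gives partial protection to the relationship table, but none to overall incidence.
- Safety is descriptive (SAP 9.12), and Week 16 follow-up is deliberate because of the long half-life.

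All of this stands, but none of it supplies a TEAE comparison ending at Day 28. Protocol 5.4.3 supports such a cut: it considers residual exposure after Day 28 unlikely to matter pharmacologically and reports no evidence of related events emerging later.

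**Conclusion.** The gap is real and cheap to close. No prespecified TEAE table ends before the Day 28 scabicide, and that exposure will be unequal by arm if moxidectin is effective. At the planning rates, with an assumed 25% to 100% of non-cured subjects treated and the same share in each arm, 7.5 to 30 of 50 placebo subjects and 3.75 to 15 of 50 per moxidectin arm would receive a scabicide.

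It might be inferred that the TEAE comparison is biased by a known amount in moxidectin's favour. The documents do not support this: they give no Day 28 mite-positive rate and no scabicide TEAE rate, and treating persistent scabies could lower later events. Nor does it follow that the main safety comparison should be censored at first scabicide. Follow-up would then be unequal and dependent on outcome, and shorter on placebo if moxidectin works.

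**What to change.** In SAP 9.12.1.3, before the Day 42 blind break:

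- Add an interval from Day 0 to the Day 28 visit (onset before that visit) to the overall TEAE summary and to the SOC/PT, severity, relationship and SAE tables.
- Flag TEAEs with onset after first scabicide use at any time. Use before Day 28 is included because the added interval does not remove it. The definition in SAP 7 needs a companion term covering use from Day 28.
- Show by arm the number of subjects who received any scabicide before Day 28 and from Day 28 onward.
- Keep the Day 42 and Week 16 tables, and do not make a comparison censored at first scabicide the primary one.
- State which interval takes an onset on the visit date itself. As written, a new event on the date of the Day 42 visit falls in neither of the two adjoining intervals.

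The cost is one extra table set, and the added tables cover a shorter interval. AE onset and concomitant medication dates are already collected, though some medication dates may be unknown (SAP 9.4.2), so a rule for those is needed. Treatment rules, endpoint and power are unchanged.

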9.12.2 Vital Signs

Aggregate summary statistics for respiratory rate, heart rate, temperature (oral and aural) and blood pressure (systolic and diastolic) will be provided for Baseline and post-Baseline

CONFIDENTIAL

assessments along with the changes from Baseline by SfAS treatment group and time point. Means, medians, SDs, minimums and maximum values will be provided.

All vital signs data, including height and weight, will be listed.

9.12.3 Clinical Laboratory Assessments

All laboratory values (hematology and serum chemistry) will be converted to the International System of Units (SI) for the purposes of summary and listing.

Hematology and serum chemistry data will be listed separately including change from Baseline and flagging all out-of-range values. Toxicity grades will be derived where possible for each hematology and biochemistry result as described in Appendix 1 of the current protocol (The 2007 FDA Guidance for Industry: Toxicity Grading Scale for Healthy Adult and Adolescent volunteers Enrolled in Preventive Vaccine Clinical Trials). Those grades will be included in the listings.

Aggregate summary data for hematology and serum chemistry test results will be provided for Baseline and post-Baseline assessments. These analyses will include changes from Baseline, to be presented only for subjects with non-missing assessments at both timepoints. Means, medians, SDs, minimum, and maximum values will be provided for both test results and for the individual change from Baseline.

A summary tabulation will show the number and proportion of subjects for the serum and hematology laboratory abnormalities graded using the scales shown in Appendix 1 of the current protocol.

9.12.4 12-Lead ECGs

An overall summary table will be provided for normal and abnormal 12-lead ECGs in the SfAS and in the PK Analysis set for the Hour 3 ECG. Abnormal 12-lead ECGs will be summarized by treatment group and overall and by whether they were normal/abnormal and if abnormal, clinically significant or not significant. ECG data are collected at Baseline and Week 16 only for subjects not selected for the PK Analysis set.

All 12-lead ECG data will be listed.

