9.4.5 Electrocardiograms

Twelve-lead ECGs will be performed before blood collection after the subject has been supine for approximately 10 minutes. ECGs will be performed in triplicate at Baseline (before randomization). After IP administration, another ECG will be performed at 3 hours (± 30 minutes) for the subjects in the PK subset. At Week 16, ECGs will be performed for all subjects. Repeat measurements will be performed if there are any abnormalities observed or artifacts are present. All ECG recordings will be reviewed by the Investigator or nominee and retained in the subject's study records.

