9.4.8 Pharmacokinetic Sampling

Blood samples for assessment of moxidectin concentrations in plasma will be collected from subjects in the PK subset. The PK subset will include approximately 20 subjects selected from each study arm. To ensure the study drug allocation remains blinded, subjects from all arms of the study will be sampled. At the end of the study, only the samples from subjects allocated to one of the three moxidectin doses will be analyzed.

Blood samples from the selected subjects will be collected post-dose at 3 hours (\pm 30 minutes) and 10 hours (\pm 2 hours) on Day 0, and on Day 28 and Day 42. All samples will be collected as close to the scheduled timepoint as possible. Actual time of sample collection will be recorded in the subject clinic notes and CRF.

Directions for processing and shipping the plasma samples can be found in the SRM.

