5 RANDOMIZATION AND BLINDING

5.1 Randomization

A unique subject number was allocated to each subject who provided written informed consent. The subject number was allocated sequentially by site. Subjects who failed screening and were approved to be rescreened retained their original subject number.

On Day 0, eligibility was reconfirmed prior to subject randomization using an Interactive Response Technology (IRT) system when each subject was assigned a unique randomization number.

Within the IRT system, the randomization of subjects to treatment is stratified by region (United States [US] and Latin America). Within each region, a permuted block randomization algorithm reflecting an equal allocation ratio among the 4 treatment cohorts of 1:1:1:1 was derived. The algorithm within each region was independent and may consist of randomly varying block sizes. Block sizes were not revealed to sites or Sponsor personnel involved in the conduct of the study. The algorithm was generated by an unblinded statistician who was otherwise independent of the study at the time the code was generated.

A subset of approximately 20 subjects will be randomly selected from each arm to provide sparse blood samples for PK analyses. To ensure the study drug allocation remains blinded, subjects from all arms of the study will be sampled.

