There will be no imputation for this endpoint. The denominator for the proportion will be subjects in each treatment group with a non-missing data point for this assessment, with subjects exposed to scabicides prior to their Day 28 assessment excluded from the analysis.

- **Plasma concentrations of moxidectin in a subset of index subjects selected for sparse PK sampling**

Approximately 20 subjects from each of the moxidectin cohorts (but not placebo) will be selected for sparse PK sampling. Moxidectin plasma concentrations will be determined at four time points, e.g., Day 0 (3- and 10-hours post-dose), Day 28, and Day 42. No pre-dose sample will be collected. Missing plasma concentrations will not be imputed.

- **The proportion of index subjects demonstrating all features of Complete Cure without regard to pruritus**

This endpoint is similar in definition as the primary efficacy Complete Cure endpoint except the pruritus component is not included in the definition, e.g.,:

- (1) Clinical cure (all signs and symptoms have completely resolved, including burrows and inflammatory/noninflammatory lesions).

and

- (2) Microscopic or dermatoscopic cure demonstrating the absence of mites, eggs, and/or scybala, and negative dermoscopy for burrows.

This will be derived from the individual assessments captured on the Day 28 Scabies Assessment eCRF page where:

- Lesion count is 0, and,
- Pruritus is ‘Present’ or ‘Absent’, and,
- Mites are ‘Absent’, and,
- Eggs are ‘Absent’, and,
- Scybala are ‘Absent’, and,
- Burrows (by dermoscopy) are ‘Absent’.

There will be no imputation for this endpoint except for subjects exposed to scabicides prior to their Day 28 assessment, who will be imputed as a non-responder (not cured). The denominator for the proportion will be subjects in each treatment group with a non-missing data point for this assessment.

- **The proportion of index subjects achieving clearance for each individual component of the Complete Cure endpoint**

This endpoint will examine each of the assessments captured on the Day 28 Scabies Assessment eCRF page individually. Subjects may be included in more than one component.

- Lesion count is 0, or,
- Pruritus is 'Absent', or,
- Mites are 'Absent', or,
- Eggs are 'Absent', or,
- Scybala are 'Absent', or,
- Burrows (by dermoscopy) are 'Absent'.

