6.4 Safety Endpoints

- Incidence and severity of treatment emergent adverse events (TEAEs).
- Incidence of serious TEAEs.
- Incidence of TEAEs leading to study withdrawal and/or death.
- Incidence of TEAE attribution of relatedness to study drug.
- Changes from Baseline in 12-lead electrocardiograms (ECGs), laboratory assessments and vital signs.

Unless otherwise noted incidence refers to subject incidence.

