8.6 Pharmacokinetic Analysis Set

The Pharmacokinetic Analysis Set will include all index subjects who received at least one dose of moxidectin and provided at least one quantifiable post-dose plasma PK concentration.

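### SAP 9.12.4 summarises the Hour 3 ECG in the PK Analysis Set, which by definition holds no placebo subjects, and it specifies no change from Baseline

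*SAP*

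**What the plan says.** **Analysis set.** SAP 9.12.4 plans an overall table of normal and abnormal "12-lead ECGs in the SfAS and in the PK Analysis set for the Hour 3 ECG". SAP 8.6 defines the PK Analysis Set as "all index subjects who received at least one dose of moxidectin and provided at least one quantifiable post-dose plasma PK concentration"; Protocol 15.3.4 has the same definition. SAP 8.3 makes the Safety Analysis Set (SfAS) the default for safety unless a section says otherwise.

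**Who has the ECG.** Protocol 9.4.5 says that after dosing "another ECG will be performed at 3 hours (± 30 minutes) for the subjects in the PK subset". That subset is about 20 subjects per arm. SAP 5.1 adds: "To ensure the study drug allocation remains blinded, subjects from all arms of the study will be sampled". On the assays, Protocol 9.4.8 says that "only the samples from subjects allocated to one of the three moxidectin doses will be analyzed". SAP 6.3 describes the sampling differently: "Approximately 20 subjects from each of the moxidectin cohorts (but not placebo) will be selected for sparse PK sampling".

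**Endpoint.** SAP 6.4 lists among the safety endpoints "Changes from Baseline in 12-lead electrocardiograms (ECGs), laboratory assessments and vital signs". Protocol 6.2.1 names ECG changes among the primary safety endpoints, and the primary safety objective is a comparison of each dose with placebo. Protocol 15.6.4.3 has ECGs analysed in the same way as laboratory data, for which Protocol 15.6.4.2 allows for changes from Baseline and/or shift tables. SAP 9.12.4 specifies normal or abnormal and, if abnormal, whether clinically significant. It does not mention change from Baseline.

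**The concern.** The Hour 3 ECG is the only scheduled post-dose ECG close to peak exposure. Protocol 5.3.2.1 puts the median time of peak concentration at 3 to 4 hours in the fasted state, and Protocol 5.4.3 gives 3.0 hours for scabies patients. The only other scheduled post-dose ECG is at Week 16, which Protocol 5.4.3 equates to about five half-lives. A drug-related ECG effect that follows plasma concentration would be looked for at Hour 3.

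A table restricted to moxidectin recipients does not serve an objective that compares each dose with placebo. Membership would also depend on an assay result that has no bearing on whether an ECG is valid safety data.

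Without a Baseline-to-post-dose cross-classification, nothing in SAP 9.12.4 separates an abnormality present before dosing from one that appeared afterwards. Such subjects can be enrolled: Exclusion 7 removes only findings that are clinically relevant and that the investigator judges to raise risk, confound evaluations or interfere with conduct.

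**Working it through.** The plan states no figure to reproduce here. The check is a comparison of definitions and a count.

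**Inputs**

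- PK subset: about 20 per arm, four arms (Protocol 9.4.8 and 10.1; SAP 5.1; footnote 6 to the SAP schedule).
- Hour 3 ECG: all subjects in the PK subset (Protocol 9.3.2 and 9.4.5; footnote 4 to the schedule).
- PK Analysis Set: a moxidectin dose and a quantifiable concentration (SAP 8.6).
- Samples assayed: moxidectin arms only (Protocol 9.4.8).

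**Can a placebo subject qualify?** No. The subject fails the first condition, having received no moxidectin. The subject also fails the second, because the sample is not assayed.

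**Count at Hour 3**

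| | PK subset | PK Analysis Set |
|---|---|---|
| Moxidectin, three arms | 3 × 20 = about 60 | at most about 60 |
| Placebo | about 20 | 0 |
| Total | 4 × 20 = about 80 | at most about 60 |

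Left out: 80 − 60 = about 20 ECGs, or 20/80 = 25% of those recorded and all of the placebo ones. The 60 is an upper bound, because any moxidectin subject with no quantifiable sample is also removed.

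**A timing consequence.** SAP 1.2 and 9.1.1 allow the PK data to be unblinded and analysed only with the Week 16 output. If that option is taken, membership of a set that depends on assay results may not be known when the Day 42 safety tables are produced.

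**Change from Baseline, section by section**

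- Vital signs (SAP 9.12.2): change from Baseline specified.
- Laboratory data (SAP 9.12.3): change from Baseline specified.
- ECGs (SAP 9.12.4): status and clinical significance only.

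SAP 6.4 names all three in one endpoint defined as change from Baseline. SAP 1.2, which lists departures from the protocol's analyses, does not mention dropping it for ECGs.

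**Who is sampled.** SAP 5.1, footnote 6 to the SAP schedule and Protocol 9.4.8 sample all four arms. SAP 6.3 excludes placebo from selection. Both cannot be right as written.

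**The case against.** The strongest reply is that this is a naming slip. The same SAP section speaks of subjects not selected for the PK Analysis Set. Nobody is selected into a set defined by a measurable concentration; selection happens at randomization, into the PK subset. The section also asks for summaries by treatment group and overall, and SAP 9.1 lists placebo among the standard columns. One could even read the SfAS table as already covering Hour 3. This is persuasive as to intent, and it stands. It does not remove the problem, because the section uses a defined term, and a programmer who applies SAP 8.6 will produce a table with no placebo column.

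A reader might go further and infer that the placebo comparison at Hour 3 is lost. The documents do not support that. The placebo ECGs are recorded, SAP 9.12.4 lists all ECG data, and SAP 9.12 permits further safety analyses if labelled post hoc. What is missing is a pre-specified summary. Nor is it an effect of this wording that the other roughly 200 − 80 = 120 subjects have only the Week 16 ECG after dosing; that is an openly stated design choice.

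A reader might also infer from SAP 6.3 that sampling only moxidectin subjects would reveal active treatment. That is not shown. Selection runs through the interactive response system (Protocol 10.1), SAP 5.1 repeats that all arms are sampled, and SAP 1.1 supersedes the protocol only on statistical methods. The SAP 6.3 sentence sits under the concentration endpoint and probably describes which arms are assayed.

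On change from Baseline, it is fair to say that the table layouts are in a separate document not available here, that Baseline ECGs exist for the comparison, and that the protocol's wording on shift tables is permissive. SAP 9.12.4 also already splits abnormal ECGs by clinical significance. So it cannot be said that old abnormalities will be reported as new ones, only that the SAP does not specify the analysis its own endpoint requires.

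Finally, Protocol 5.3.2.2.1 reports a placebo-controlled QT study with no significant effect up to 36 mg. That lowers the prior concern, but it was in healthy volunteers with 10 per group, and this trial made its own placebo comparison a primary objective.

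**Conclusion.** The point holds as a defect in the SAP text. Taken literally, the Hour 3 ECG summary has no placebo subjects and covers at most about 60 of about 80 recorded ECGs. The ECG section also lacks the change-from-Baseline analysis that defines the endpoint. The PK subset was probably intended. The data are collected and listed, and neither a blinding risk nor an irrecoverable loss is demonstrated. The matter is worth correcting because it affects a primary safety endpoint at the scheduled ECG nearest peak exposure, but it does not threaten the trial.

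The counts assume the planned 20 or so subjects per arm in the PK subset, with each Hour 3 ECG actually taken. They also assume that all four arms are sampled, as Protocol 9.4.8 and SAP 5.1 say.

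**What to change.** 1. In SAP 9.12.4, summarise the Hour 3 ECG in SfAS subjects selected for the PK subset, all four arms, by actual treatment received. Define that subset by name in SAP section 8, and keep the PK Analysis Set for concentration summaries. Change the later sentence in 9.12.4 about subjects not selected to refer to the subset as well.
2. Add shift tables with three categories (normal, abnormal not clinically significant, abnormal clinically significant): Baseline to Hour 3 in the PK subset, and Baseline to Week 16 in the SfAS.
3. Reconcile SAP 6.3 with SAP 5.1 and Protocol 9.4.8, so that the text says subjects in all four arms are sampled and only moxidectin samples are assayed.

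The cost is a few lines of SAP text and modest table programming. No new data, visits or procedures are needed. The change should be made before the blind is broken for the Day 42 analysis, so that the Hour 3 comparison is pre-specified and not post hoc.
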